9.3.1 AE Follow-up

All AEs occurring during the study are to be followed up in accordance with good medical practice until they are resolved, stabilized or judged no longer clinically significant or, if a chronic condition, until fully characterized. Any AEs that are considered drug-related (possibly related, definitely related) must be followed for 30 days, or to resolution, or until no improvement is expected, whichever occurs first.

9.3.2 Overdose

No information on treatment of overdose of Ampion is currently available. In the case of overdose, the patient should be followed as an AE and appropriate supportive medical treatment instigated.

9.4 Serious Adverse Event Reporting

9.4.1 Reporting Requirements

Unexpected serious suspected adverse reactions are subject to expedited reporting to FDA. All SAEs must be entered into the eCRF within 24 hours of first knowledge of the event by study personnel. It is important that the investigator provide his/her assessment of relationship to study drug at the time of the initial report. Entry of an SAE into the eCRF triggers an automatic alert to the CRO safety team. The following information must be reported:

- Protocol number
- Site and/or Investigator number
- Patient number
- Demographic data
- Brief description of the event
- Onset date and time
- Resolution date and time, if the event resolved
- Current status, if event not yet resolved
- Any concomitant treatment and medication
- Investigator's assessment of whether the SAE was related to Investigative product or not

The CRO Safety Associate will contact the site for clarification of data entered onto the eCRF, or to obtain missing information. In the event of questions regarding SAE reporting, the site may contact the appropriate individual as in Section 9.4.2.

9.4.2 SAE Contact Information

Ampio Main Line: 1 [contact]

Ampio Pharmaceuticals, Inc., or their designee CRO, is responsible for submitting reports of AEs associated with the use of the drug that are both serious and unexpected to FDA according to 21 CFR 312.32 and the final guidance (2012). All investigators participating in ongoing clinical studies with the study medication will receive copies of these reports for prompt submission to their Institutional Review Board (IRB) or Ethics committee (EC).

10 STATISTICAL METHODS

10.1 General Considerations

This section describes the rules and conventions to be used in the presentation and analysis of the data. A comprehensive presentation of the data management and statistical analysis plan will be approved by Ampio Pharmaceuticals, Inc. prior to unblinding of study data.

10.2 Study Objectives

The co-primary trial objectives are to evaluate the greater efficacy for pain improvement and function improvement of 4 mL Ampion versus 4 mL saline IA injection when applied to patients suffering from severe OAK. Efficacy will primarily be assessed with WOMAC A pain and WOMAC C function scores.

The secondary trial objectives include the following evaluations of an intra-articular injection of Ampion, as compared to saline, when administered to patients suffering from severe OAK: improvement in the 100 mm VAS Pain scale; assessment of safety; improvement in the Patient Global Assessment; the amount of rescue analgesia.

Exploratory objectives are to analyze the effect, if any, of the efficacy of Ampion, as compared to saline, on stiffness; OMERACT-OARSI responder status; proportion of treatment failures; change in pain and function will be examined as a CDF plot for Ampion and saline treated patients; and a Bayesian meta-analysis for LK WOMAC A pain sub score including KL 4 patients from studies AP-003-A, AP-003-B, AP-003-C, AP-004, and AP-013. Analysis with biomarkers, such as those for analgesic use and chemokines and cytokines associated with inflammation and cartilage regeneration, may be analyzed to compare differences between treatment groups using urine samples collected at Week 12.

10.3 Analysis Populations

10.3.1 Safety Analysis Population:

The safety analysis population is defined as all patients who are randomized and receive study medication (Ampion or saline). Patients will be analyzed as treated.

10.3.2 Intent-to-treat Population:

The intent-to-treat (ITT) analysis population is defined as all patients who are randomized. All efficacy analyses will be performed in the ITT population. Patients will be analyzed as randomized.

10.3.3 Per Protocol Population:

The per protocol analysis population is defined as all patients included in the ITT analysis who met all entry criteria and had no major protocol violations. All efficacy analyses will be repeated

in the per-protocol population. These analyses will be supportive of the ITT analysis. Patients will be analyzed as treated.

10.3.4 Statistical Analysis of Co-Primary Effectiveness Endpoints

A mixed-effects model with repeated measures (MMRM) will be used to test the main effect of change in WOMAC A weekly pain score (determined as the average of Daily Pain measurements taken at Baseline and Week 12) from Baseline of Ampion vs. saline at 12 weeks. The model will include change from Baseline measures at 2, 4, 6, 8, 10, and 12 weeks. Treatment assignment, week, and Baseline WOMAC A measure will be included as fixed effects. Patient ID will be included to capture repeated measures using a compound symmetric covariance matrix for residuals. The primary hypothesis test for pain is the change in pain at 12-weeks at the one-sided $\alpha = 0.025$ level.

The same model will be used to test the effect of WOMAC C function change from Baseline of Ampion vs. saline at 12 weeks. WOMAC C will be tested at one sided $\alpha = 0.025$. Because both endpoints have to achieve statistical significance, this pairing ensures the one-sided Type I error control at the 0.025 level.

10.3.5 Primary Hypotheses

The trial has co-primary hypotheses – requiring success on both for a successful trial. First, pain reduction must be demonstrated for Ampion vs. saline control. Next a function improvement must be shown on Ampion vs. saline control.

Reduction in Pain, as measured by a change in the WOMAC A pain sub score as measured by the 5-point Likert scale between Baseline and Week 12, will be greater in patients treated with Ampion than with saline:

- Null Hypothesis: $\mu_A = \mu_S$
- Alternate Hypothesis: $\mu_A < \mu_S$

Where μ_A = mean pain reduction in Ampion arm; μ_S = mean pain reduction in saline arm. Lower mean change scores indicate greater pain reduction.

Improvement in function, as measured by a reduction in the WOMAC C function sub score as measured by the 5-point Likert scale between Baseline and Week 12, will be greater in patients treated with Ampion than with saline:

- Null Hypothesis: $\mu_A = \mu_S$
- Alternate Hypothesis: $\mu_A < \mu_S$

Where μ_A = mean function reduction in Ampion arm; μ_S = mean function reduction in saline arm.

10.3.6 Definition of Study Visits

This clinical trial has a total of 11 study visits, including telephone contacts, during the 24-week study (see Table 6.1). The time-on-study for each patient observation will be defined relative to Day 0, the day of the initial dose. For analysis, the Baseline measure is the latest measure prior to initiation of treatment. For analysis of Baseline WOMAC A pain, the Baseline pain score is the average of all scores measured during days -6 to 0, prior to injection of treatment. For analysis of Week 12 WOMAC A pain, the Week 12 pain score is the average of all scores measured during the seven days prior to and including the Week 12 office visit.

10.3.7 Number of patients to receive study drug

This study is designed to enroll 1,034 patients, 517 per study arm, randomized 1:1 for Ampion and saline. There will be an interim analysis at 724 patients, 362 per study arm, randomized 1:1, Ampion and saline.

Following the interim analysis, the trial will either a) continue up to a total of 1,034 patients, 517 patients per study arm, randomized 1:1 for Ampion and saline IA injection; b) allow for sample size re-estimation up to 1.5 times the original trial size for a total of 1,552 patients, 776 per study arm, randomized 1:1 for Ampion and saline IA injection.

10.3.8 Disposition of patients

Disposition of patients, including study completion status and response to therapy as measured by WOMAC pain sub scores, will be summarized by treatment group (Ampion and saline), age group, race and gender for each of the analysis populations.

10.3.9 Interim analysis

There will be one interim analysis once 724 subjects have reached the primary endpoint assessment at Week 12.

At the interim analysis, the conditional probability based upon the observed treatment WOMAC C function score will be calculated. The minimal conditional probability that allows a sample size increase without inflating Type I error under the promising zone for a sample size increase up to 150% is 0.391. Any conditional power < 0.391 results in going to 1,034 patients, randomized 1:1 for Ampion and saline IA injection. Sample size re-estimation according to the promising zone is done for conditional powers between 0.391 and 0.90 with a sample size increase capped to a maximum of 1,552 total patients, randomized 1:1 for Ampion and saline IA injection. A conditional power $> 90\%$ results in enrolling to 1,034 patients.

The final analysis, defined by a sample size established using the promising zone, will use the critical value with one-sided $\alpha = 0.025$ for WOMAC A (Ampion vs. saline control) and WOMAC C (Ampion vs. saline control).

10.3.10 Blinding and randomization

Patients will be assigned to treatment by a randomization schedule generated by an independent statistician. Ampion and saline will be provided in study vials labeled with the appropriate information and packed into patient kits.

Where required, safety personnel may be unblinded to a particular patient's treatment assignment to meet reporting requirements to Regulators. Unblinding may occur by contacting Ampio Pharmaceuticals, Inc.

A final Statistical Analysis Plan will be issued prior to unblinding at the interim analysis of data to adjust for any changes to the protocol or unexpected issues in study conduct and data that affect the planned analyses.

10.3.11 Data presentation

10.3.11.1 Demographic and Baseline Characteristics

Demographic (e.g., age, sex, race, ethnicity) and Baseline characteristics (e.g., weight, height) summarized using descriptive statistics, overall and by treatment group for the ITT analysis population.

10.3.11.2 Medical History and Physical Examination

The number and percent of patients with past and current medical disorders at the time of randomization will be presented overall and by treatment group for the ITT analysis population. Results of any abnormalities documented from the abbreviated physical examination at Baseline and Week 12 and Week 24, will be summarized overall and by treatment group for the safety and ITT analysis populations.

10.3.11.3 Concomitant Medications or Treatments

The number and percent of patients receiving concomitant medications or treatments prior to, during the study and at the final visit will be tabulated and presented overall and by treatment group for the ITT analysis population. Concomitant medications/treatments will be summarized using descriptive statistics and will be presented by type of drug (WHO drug classification) overall and by treatment group for the safety and ITT analysis populations.

Treatment failures are defined as patients who receive additional medications or surgical procedures in order to treat worsened symptoms in the treated knee during the study; specifically, treatment failures are any patients who:

- Increase their corticosteroid dose of ≤ 10 mg above their starting dose of corticosteroid during the study to treat worsened symptoms in the treated knee;
- Increase use of NSAID pain medications by a clinically significant amount during the study to treat worsened symptoms in the treated knee;
- Begin opioid treatment during the study to treat worsened symptoms in the treated knee;
- Receive intra-articular injection of pain medicine in the treated knee during the study to treat worsened symptoms in the treated knee;

- Undergo total knee replacement or other surgical procedure in the treated knee prior to assessment of the primary efficacy endpoint.

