8.3 Concomitant Treatments and Rescue Medication

The following medications / therapies are NOT allowed during this clinical study:

1. No IA injected pain medications in the study knee during the study.
2. No analgesics containing opioids.
3. No NSAID use during the 48 hours prior to efficacy evaluations.
4. No clinically significant increase in NSAID use above baseline/pre-study dosing levels to treat worsened symptoms in the treated knee.
 - a. NSAID use during the study may be continued at baseline/pre-study dosing levels and may be increased or decreased if clinically indicated; acetaminophen is also available as a rescue medication during the study from the provided supply.
5. No non-pharmacological treatment targeting OA started or changed during the study.
6. No topical treatment on osteoarthritis index knee during the study.
7. No significant anticoagulant therapy (e.g. Heparin or Lovenox) during the study (treatment such as Aspirin or Plavix is allowed).
8. No systemic treatments that may interfere with safety or efficacy assessments during the study.
9. No immunosuppressants.
10. No use of corticosteroids > 10 mg prednisolone equivalent per day.
 - a. If corticosteroid use is \leq 10 mg prednisolone equivalent per day, and if clinically indicated, subjects should be allowed to decrease their corticosteroid use. Additionally, some subjects may need to increase their steroid dose to treat worsened symptoms in the treated knee, and subjects who increase their corticosteroid dose above their starting dose of corticosteroid during the study will be treated as “treatment failures” for efficacy analysis.
11. No human albumin treatment during the study.

Any medication used during the study should be recorded. All concomitant medication start and stop dates, total daily dose, route and indication should to be recorded.

The only allowed rescue medication is 500 mg of acetaminophen (paracetamol), one tablet every four hours as required by the patient.

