10.4.5 Sensitivity Analysis

The two co-primary endpoints and three efficacy secondary endpoints will be re-analyzed separately in the per-protocol population to exclude treatment failures.

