### **End of Study**

End of study is at Visit 10 (Week 24), unless terminated early.

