## **Treatment failure**

Treatment failures are defined as patients who receive additional medications or surgical procedures in order to treat worsened symptoms in the treated knee during the study; specifically, treatment failures are any patients who:

- Increase their corticosteroid dose of  $\leq 10$  mg above their starting dose of corticosteroid during the study to treat worsened symptoms in the treated knee;
- Increase use of NSAID pain medications by a clinically significant amount during the study to treat worsened symptoms in the treated knee;
- Begin opioid treatment during the study to treat worsened symptoms in the treated knee;
- Receive intra-articular injection of pain medicine in the treated knee during the study to treat worsened symptoms in the treated knee;
- Undergo total knee replacement or other surgical procedure in the treated knee prior to assessment of the primary efficacy endpoint.

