#### **6.1.3 Per Protocol (PP) Analysis Set**

The per protocol (PP) analysis population is defined as all patients who met all entry criteria and had no major protocol violations. All efficacy analyses will be repeated in the PP population. These analyses will be supportive of the ITT analysis. Patients will be analyzed as treated. No imputations will be performed.

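### Treatment failures are counted to Week 24 but excluded from Week 12 analyses, so the per-protocol sensitivity re-analysis can drop valid Week 12 scores because of later events

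*Protocol*

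**What the plan says.** Protocol 10.3.11.3 lists five ways to become a treatment failure. The lead-in and the first four bullets (steroid, NSAID, opioid, intra-articular injection) cover the whole study; the steroid bullet, for example, reads "Increase their corticosteroid dose of ≤ 10 mg above their starting dose of corticosteroid during the study". The fifth is different: "Undergo total knee replacement or other surgical procedure in the treated knee prior to assessment of the primary efficacy endpoint". SAP 5.2 repeats the list, again with the steroid increase counted "above their starting dose of corticosteroid during the study to treat worsened symptoms in the treated knee". The SAP also fixes how long the study lasts: "End of study is at Visit 10 (Week 24), unless terminated early".

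The definition is used in the sensitivity analysis. Under protocol 10.4.5, the two co-primary and three secondary efficacy endpoints are "re-analyzed separately in the per-protocol population to exclude treatment failures". SAP 3.6 and 8.6.4 say the same. None of the three places gives a time limit. SAP 6.1.3 adds that nothing is imputed in the per-protocol set, so an excluded patient's Week 12 scores are lost to that analysis.

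Two related rules also have no Week 12 limit. The steroid rule appears again in exclusion criterion 12h (synopsis and 4.4) and in 8.3 item 10a. Section 8.3 prohibits opioids, intra-articular pain medication and, in its words, "No clinically significant increase in NSAID use above baseline/pre-study dosing levels to treat worsened symptoms in the treated knee". The per-protocol set keeps patients "who met all entry criteria and had no major protocol violations" (SAP 6.1.3 agrees), and neither document defines or dates a major violation.

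The one failure rule with a Week 12 label is a separate exploratory endpoint, the proportion of failures at Week 12 (protocol 3.5.3 and 10.4.3, SAP 3.3).

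**The concern.** A patient may have complete Week 12 scores and then raise a steroid dose for the treated knee at Week 16. As written, that patient is a failure and leaves the Week 12 re-analysis. A patient who has that knee replaced at Week 16 stays in. Neither document gives a reason for the difference.

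The re-analysis is there to show whether the Week 12 result holds without patients who needed other treatment. Treatment that starts after Week 12 cannot have altered the Week 12 pain, function or VAS score. It may well depend on that score, because patients who are doing badly seek more treatment. Excluding on it therefore selects patients partly on the outcome, and the remaining arms need not be comparable.

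**Working it through.** **1. Windows compared.** Four of five bullets run to Week 24; one stops at Week 12. On the schedule's visit days, the part after the endpoint is (174 - 84)/174 = 52% of follow-up; in nominal weeks it is 12/24 = 50%.

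**2. The plan's own figures.** For pain the plan assumes a difference of 0.83 - 0.62 = 0.21, SD 0.85 and one-sided alpha 0.025. Patients per arm for 90% power: 2 × (1.960 + 1.282)² × 0.85² / 0.21², which rounds up to 345, or 690 in total, as stated. Power is 0.978 at 517 per arm and 0.972 at 492, against a stated 97%. In SD units the pain effect is 0.21/0.85 = 0.247. The function effect implied by 984 patients at 90% power is (1.960 + 1.282) × √(2/492) = 0.207 SD.

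**3. Patients dropped only for later events.** The documents give no failure rate. Let p be the assumed risk by Week 24, at a constant rate. The share failing only after Week 12 is √(1-p) - (1-p).

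| p | Failing only after Week 12 | Of 1,034 patients |
|---|---|---|
| 0.05 | 2.5% | about 26 |
| 0.10 | 4.9% | about 50 |
| 0.20 | 9.4% | about 98 |

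**4. Effect on the estimated difference, same dependence in both arms.** Take the Week 12 change as normal with equal SD in each arm, centred at -d/2 (Ampion) and +d/2 (saline) in SD units, higher being worse. The probability of late failure is logistic in the score, with slope ln(OR) per SD and one intercept for both arms, set so that the average equals the share in step 3. The difference among those who remain is the gap in E[X(1-P)]/E[1-P], where X is the score and P the late-failure probability. Removal of failures up to Week 12 and other per-protocol exclusions are left out.

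| p | OR 1.5 | OR 2 | OR 3 |
|---|---|---|---|
| 0.05 | 0.209 (-0.4%) | 0.208 (-1.1%) | 0.205 (-2.6%) |
| 0.10 | 0.208 (-0.7%) | 0.206 (-2.1%) | 0.200 (-4.6%) |
| 0.20 | 0.207 (-1.4%) | 0.202 (-3.6%) | 0.194 (-7.7%) |

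Entries are the pain difference, starting from 0.210. Function shows the same percentage losses to within rounding. At p = 0.02 the loss is 0.2-1.1%.

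**5. The same model with arms that differ.** Multiply the odds of late failure on Ampion by 1.5 at any given score (an assumption) and keep the same overall share. At p = 0.10 and OR 2 the pain difference rises from 0.210 to 0.216. Over p = 0.05-0.20 and OR 1.5-3 it grows by 1.2-5.0% for pain and 1.5-6.6% for function. Divide the Ampion odds by 1.5 instead, and the same middle case falls to 0.196. The sign and size in step 4 therefore depend on the equal-intercept assumption.

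**6. Power.** A comparison with 0.978 (pain) or 0.914 (function) at 517 per arm would mislead, because the corrected rule still removes failures up to Week 12. Removing only those at random leaves 517 × √(1-p) per arm, or 504 to 462 for p = 0.05-0.20. That alone gives about 0.975-0.964 for pain and 0.907-0.882 for function. Much of any fall from the no-removal figures, and nearly all of it at low odds ratios, is thus ordinary loss of patients.

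**The case against.** The best defence is that the intent can be read. The only failure endpoint analysed is labelled Week 12, the surgery bullet has the same limit, and SAP 10.2 lists treatment failures and reasons for exclusion by patient, so late exclusions could be traced. That lowers the stakes. It does not supply the missing rule: the Week 12 label belongs to a separate proportion and is not carried into the definition or the exclusion, and the repeated steroid sentences point the other way.

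A second objection stands in full. A reader might infer that all five re-analysed endpoints are affected. They are not. SAP 8.6.2 fits PGA on visits through Week 24 with no treatment-by-week term, and compares pill counts over the whole study. (Protocol 10.4.2 and SAP 8.6.7 describe rescue use to Week 12.) As SAP 8.6.2 is written, treatment at Week 16 can affect both results, so a study-wide failure rule has a rationale there. The point is clean only for pain, function and VAS.

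Third, removal through the per-protocol definition is conditional: it needs a breach after Week 12 to be classed as major, and the documents do not say whether it would be. It matters here because correcting only the failure exclusion could leave that route open for opioids, injections and NSAID increases.

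**Conclusion.** The point holds for the Week 12 co-primary and VAS re-analyses. As written, the rule removes valid scores because of events after they were measured, and it treats surgery differently from other treatment without a stated reason. It deserves correction before unblinding, but its reach is small: the primary ITT analysis, type I error and sample size are untouched.

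Size and direction are unknown. With 5-20% failing by Week 24 at a constant rate, 2.5-9.4% of patients would be dropped only for later events. The co-primary differences would shrink by 0.4-8% if late failure depends on the Week 12 score equally in both arms; the top of that range needs both a 20% failure rate and an odds ratio of 3. A reader might infer that the gap always pulls toward no difference, or that it favours Ampion. The documents support neither, because they give no late-failure rate by arm and a modest imbalance changes the sign.

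**What to change.** 1. Keep one study-wide failure definition in protocol 10.3.11.3 and SAP 5.2, and put the time limit in the analysis rules. In protocol 10.4.5 and SAP 3.6 and 8.6.4, state that the Week 12 co-primary and VAS re-analyses exclude only failures that start before the patient's Week 12 efficacy assessment. For consistency, the surgery bullet's own limit moves there too.
2. Use the same cut-off for the proportion of failures at Week 12, and state that it governs the steroid sentences in exclusion criterion 12h and 8.3 item 10a when they are applied to Week 12 analyses.
3. In protocol 10.3.3 and SAP 6.1.3, state that prohibited treatment started after the Week 12 assessment does not remove a patient from these Week 12 per-protocol analyses.
4. Keep the study-wide flag for analyses that use later data: the PGA model through Week 24 and the pill count over the study, as SAP 8.6.2 is written.

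The cost is a few clauses before unblinding and a second dated flag to program. No new data are needed for the medication criteria, since 8.3 already requires start dates, doses and indications.
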